### 10.8.2 Extraocular Muscle Function

The number and percentage of subjects reporting normal and abnormal test results on the Extraocular Muscle Function test will be presented by eye, visit and timepoint (pre- or post-injection, if applicable).

Extraocular Muscle Function test data will be presented in a listing.

### 10.8.3 Confrontation Visual Field

The number and percentage of subjects reporting normal and abnormal test results on the Confrontation Visual Field test will be presented by eye, visit and timepoint (pre- or post-injection, if applicable).

Confrontation Visual Field test data will be presented in a listing.

### 10.10 Height and Weight

Subjects' height and weight will be collected at Baseline and at the Month 12 visit (weight only) and recorded in a listing.

Galderma

Protocol number: 43USCH2208

Protocol V4.0

### 10.11 Urine Pregnancy Test

A urine pregnancy test will be performed at Screening and Baseline for all women of childbearing potential. At Month 1 after Baseline, a test is done only if the touch-up treatment is performed. During visits with a treatment, the test is done prior to treatment administration.

Results will be reported in a data listing that will include the date of the pregnancy test, the test result and the reason it was not done where it applies. Pregnancies reported during the study will also be presented in this data listing.

### 10.12 Vaccines

Vaccine data will be reported in a data listing that will include the type of vaccine, the name, the manufacturer, the route, the location and the date and time of administration.

### 10.13 Device Deficiencies

A device deficiency is defined as an inadequacy of a medical device with respect to its identity, quality, durability, reliability, safety, or performance. Device deficiencies will be evaluated at Baseline and if the touch-up treatment is performed.

Any reported product complaint related to device deficiency will be presented in a data listing.

## 11 Statistical/Analytical Issues

### 11.1 Handling of Missing Data

The number of missing values will be summarized and reported as appropriate in all outputs. Calculations for all questionnaires will follow the methods specified in the specific sections of this SAP for the handling of the data.

For ITT analysis of the change from Baseline based on the Blinded Evaluator's live assessment of GCRS at Month 3 after last treatment (primary endpoint), the analysis will be performed using MI as the primary imputation method. Multiple imputation methods are specified in [Section 11.6](#).

Sensitivity analyses will be performed to evaluate the impact of missing data on the primary endpoint using BOCF, worst case, and observed cases as described in [Section 9.1.3](#).

All other effectiveness endpoints will be evaluated based on the OC in the ITT analysis set. Descriptive statistics of all safety data will be performed on OC in the Safety Population.

Galderma

Protocol number: 43USCH2208

Protocol V4.0

In the event the intensity, relationship, or seriousness of an AE is missing, the most severe value will be assigned. Intensity will be assigned to “Severe”, relationship will be assigned to “Related to Study Product and Study Procedure”, and seriousness will be imputed to SAE.

## 11.2 Handling of Missing/Partial Dates

While every effort will be made to obtain full, complete information on all data collected, Table 8 outlines the imputation rules to be followed for any missing dates. Dates will be presented as collected in the listings.

**Table 8. Imputation Criteria for Missing/Partial Dates**

| Variable                            | Missing Day  | Missing Month or Day and Month   | Missing Year, Month and Year, or Day and Year   | Missing Day, Month, Year                        |
|-------------------------------------|--|--|---|---|
| Adverse Event/Medication Start Date | Assign to the first of the month (i.e., UNK-JAN-2023 becomes 01-JAN-2023)  | Assign to the month of ‘June’ (i.e., 01-UNK-2023 becomes 01-JUN-2023), provided the imputed date is on or after the subject’s Baseline study treatment date; otherwise, the subsequent month after study treatment will be used. | Assign to year of Baseline study treatment (i.e., 01-JAN-UNK becomes 01-JAN-2019), provided the imputed date is on or after the subject’s study treatment date; otherwise, the date of Baseline study treatment will be used. | Assign to Baseline study treatment date         |
| Adverse Event/Medication End Date   | Assign the last day of the month (i.e., UNK-JAN-2023 becomes 31-JAN-2023). | Assign to the subsequent month after the start date.   | Assign to the year of Baseline study treatment (i.e., 01-JAN-UNK becomes 01-JAN-2023), provided the imputed date is after the start date; otherwise, the subsequent year after start date will be used.                       | Assumed AE/medication is ongoing; no imputation |

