7.9 Adverse events

7.9.1 Definition of an Adverse Event

The definition of an AE (Medical Devices Regulation [MDR] article 2[57]): An AE is any untoward medical occurrence, unintended disease or injury, or untoward clinical signs (including abnormal laboratory findings) in subjects, users or other persons², in the context of a clinical investigation, whether or not related to the Investigational device.

This definition includes:

- a) events related to the investigational product or the reference product
- b) events related to the procedures involved
- c) events that are anticipated as well as unanticipated

The AE reporting on each subject shall start once a subject is enrolled (i.e., randomized and/or treated) in the study. All other events that occur after the subject signs the ICF but before enrollment will be recorded in the subject's medical history. The reporting shall continue during each follow-up visit (including telephone contacts and extra visits between planned visits) until the last scheduled visit in the study.

All AEs, non-serious as well as serious AEs (SAEs), are to be reported as AE in the eCRF.

A request for additional information from the Sponsor Medical Expert(s) for non-serious AEs, should be collected and answered using the Adverse Event Clarification Form.

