**10.2 Adverse Events**

Adverse Event reporting on each subject will start once a subject is enrolled in the study. All other events that occur after the subject signs the ICF but before enrollment will be recorded in the subject's medical history. The reporting shall continue during each follow-up visit (including telephone contacts and extra visits between planned visits) until the last scheduled visit in the study.

All AEs reported will be listed, documenting the verbatim term, MedDRA Preferred Term (PT) and System Organ Class (SOC), affected area, event start and end date (or ongoing), seriousness (yes/no), intensity, relationship to study product (yes/no), relationship to injection procedure (yes/no), UADE status, AESI status, action taken, outcome, time to onset, duration and Injection Timepoint. All AE endpoints will be presented Overall. The Overall Summary of Adverse Events table and the Adverse Events by System Organ Class and Preferred Term table will be presented Overall and by Injection Timepoint in which they occurred (see definition in [Section 4.5.2](#)). Additional presentations of AE endpoints may be presented by Injection Timepoint on an as needed basis.

Only AEs occurring after treatment will be included in analysis. AEs occurring before initial treatment, if any, will only be presented in data listings. Missing dates, intensity, relationship, and seriousness will be imputed as described in [Section 11.1](#) and [Section 11.2](#).

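### In SAP Table 8, the missing-day rule for AE start dates has no treatment-date floor, so a day-missing AE in the month of the initial injection can be imputed as pre-treatment and drop out of the AE summary tables

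*SAP*

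**What the plan says.** SAP Table 8 (Section 11.2) has four rules for a partial or missing AE start date.

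- Day missing: "Assign to the first of the month (i.e., UNK-JAN-2023 becomes 01-JAN-2023". No condition on the treatment date is attached.
- Month missing: June, if that is on or after Baseline treatment; "otherwise, the subsequent month after study treatment will be used".
- Year missing: the year of Baseline treatment, if the result is on or after treatment; "otherwise, the date of Baseline study treatment will be used".
- Everything missing: "Assign to Baseline study treatment date".

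SAP 10.2 sets the inclusion rule: "Only AEs occurring after treatment will be included in analysis. AEs occurring before initial treatment, if any, will only be presented in data listings". It continues: "Missing dates, intensity, relationship, and seriousness will be imputed as described in" Sections 11.1 and 11.2. Imputed dates therefore feed the AE analysis. SAP 10.2.4 also sends partial start dates to Section 11.2 and computes time to onset from the most recent prior treatment.

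Protocol 7.9.1 fixes when AE collection begins: "The AE reporting on each subject shall start once a subject is enrolled (i.e., randomized and/or treated) in the study". Events between consent and enrollment go to medical history.

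**The concern.** Three of the four start-date rules keep the imputed date on or after Baseline treatment. The missing-day rule does not, and nothing in the SAP explains the difference, so it reads as an omission.

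The resulting exclusion is nearly always wrong. Protocol 8.2 places randomization and injection in the same Baseline visit, and AE reporting starts no earlier than randomization. A reported AE dated to the injection month is therefore almost certainly post-treatment.

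The rule also runs against SAP 11.1, which takes the worst case when intensity, relationship or seriousness is missing. An AE lacking those items and its start day would be set to severe, related and serious, and then removed from the tables by its date.

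At stake are AE incidence in the summary tables, assignment to an injection timepoint, time to onset, and the listing of related AEs with onset more than 21 days after treatment.

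**Working it through.** The plan gives no figure to reproduce; this is a logic check on a date rule.

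**Inputs.** The Table 8 missing-day rule; the SAP 10.2 inclusion rule; touch-up at 4 weeks with a window of +7 days, i.e. day 28 to 35 (Protocol 8.3.3). Assumption: injection dates uniform over 365 consecutive days (1 June 2023 to 30 May 2024).

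**Single case.** Injection 14-JUN-2023, AE recorded as UNK-JUN-2023. The imputed start is 01-JUN-2023, 13 days before treatment, so the AE goes to listings only.

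**Share lost, given a missing day.** Let T be the injection date and L the true onset lag in days. The AE is lost when the 1st of the month containing T + L is earlier than T. That requires T + L to fall in the same month as T, and T not to be the 1st. For L = 0 all dates except twelve 1sts qualify: 365 − 12 = 353. For L = 1 to 28, summing over the months (the span includes a 29 February) gives 366 − 12(L + 1).

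| True onset lag | Dates lost | Share of 365 |
|---|---|---|
| 0 | 353 | 96.7% |
| 1 | 342 | 93.7% |
| 3 | 318 | 87.1% |
| 7 | 270 | 74.0% |
| 14 | 186 | 51.0% |
| 21 | 102 | 27.9% |
| 28 | 18 | 4.9% |

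Averaging with equal weight per lag day:

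- days 0-3: (353 + 342 + 330 + 318) / (4 × 365) = 1343/1460 = 92.0%
- days 0-7: 2495/2920 = 85.4%
- days 0-28: 5393/10585 = 50.9%

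**From conditional share to overall loss.** If a fraction p of AEs with onset on days 0-7 lacks the start day, the fraction lost is 0.854 × p. The documents do not give p. Purely as an illustration, p = 1% loses 0.85% of these AEs and p = 5% loses 4.3%.

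**Touch-up month.** Take touch-ups at day 28 to 35 and AEs at lags of 0, 1, 3 and 7 days that fall in the touch-up's calendar month. About 96% are imputed before the touch-up but after the initial injection, 0 to 0.9% are imputed before the initial injection and lost, and 3 to 4% stay correct. Example: initial injection 05-JUN, touch-up 03-JUL (day 28), AE on the touch-up day recorded as UNK-JUL. The imputed start is 01-JUL. A day-0 reaction to the touch-up becomes a day-26 event of the initial treatment and, if related, enters the listing of onsets beyond 21 days.

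**With a floor.** If the known month and year match Baseline treatment and the later of the 1st and the Baseline date is used, 0 of 365 injection dates give a pre-treatment start at any lag from 0 to 28 days.

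**The case against.** A reader might infer that AEs of the injection month vanish from the report, or that 97%, 85% or 51% of early AEs are undercounted. The documents support neither.

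- **Scope.** Only AEs with a missing start day and a known month and year are affected. Fully dated AEs are untouched.
- **Listings.** All AEs are listed, with dates as collected (SAP 10.2 and 11.2). Serious AEs and AEs of special interest have their own listings.
- **Frequency.** AEs are asked about at 72 hours, 14 days and 1 month, the start date is a defined eCRF item, and the SAP commits to completing dates. Early AEs are the least likely to lack a day. The percentages are conditional shares, not effect sizes.
- **Diary.** Bruising, swelling, pain, lumps and similar reactions are recorded daily for 28 days after each treatment and presented separately (Protocol synopsis, Safety Assessments).
- **SAP 4.5.2.** It puts all AEs of subjects without a touch-up into the initial-treatment timepoint, which sits awkwardly with 10.2.

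All of this limits the size, and the first four points stand. None supplies the missing floor. The diary does not replace the AE tables, and 4.5.2 does not clearly override the explicit exclusion in 10.2.

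The missing-month rule can also be criticised: a start with only the year known goes to June or the month after treatment, while a fully missing date goes to the treatment date. That makes onset arbitrary but keeps the AE in the tables, so it is secondary.

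**Conclusion.** The missing-day rule is wrong as written and should be corrected. It classes as pre-treatment nearly every day-missing AE that starts in the month of the initial injection. It also moves most day-missing AEs that follow a touch-up in the same month to the wrong injection timepoint. The shares of 97% (day 0), 85% (days 0-7) and 51% (days 0-28) rest on uniform injection dates, with onset days weighted equally within each range, and apply only when the start day is missing.

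The overall effect on AE incidence cannot be computed from the documents and may be small. The rule is the same in both arms and does not touch the primary endpoint. The point is a correction to the safety derivations, not a threat to the trial's main conclusion.

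**What to change.** Amend the missing-day start cell of SAP Table 8, for AE start dates only:

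1. If the known month and year equal those of Baseline treatment, impute the later of the 1st of the month and the Baseline treatment date, unless a known AE stop date is before Baseline treatment.
2. The imputed start must never be later than a known stop date.
3. For a touch-up month, use a known stop date to rule out onset after the touch-up, and state one fixed rule for assigning the remaining AEs to an injection timepoint.

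Keep medications out of this change. The same cell governs their start dates, and a floor would push prior medications, which SAP 8.5 defines as stopped before Screening, to the treatment date.

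A tempting alternative is to use the most recent treatment in the known month. It creates a new error: with dates and onset uniform, 52% (touch-up at day 28) or 31% (day 35) of day-missing AEs with true onset 0-27 days after the initial injection would move to the touch-up date. Without a stop-date cap it can also give negative durations.

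The cost is a few sentences in Table 8 and one derivation change, with no new data. The downside is that a few truly pre-treatment events may be counted as post-treatment, which is the cautious direction for safety.

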### 10.2.4 Time to Onset and Duration of AEs

Time to onset and duration of related AEs will be recorded. Time to onset of an AE will be derived as the AE start date minus the date of most recent prior treatment. If the AE start

Effective date: 2024-05-29 18:37

Effective

Version: 1.0

Galderma

Protocol number: 43USCH2208

Protocol V4.0

date is partially/completely missing, it will be imputed using the imputation rules specified in [Section 11.2](#).

Duration of an AE will be derived as the AE stop date minus the AE start date + 1. If the AE start date is partially/completely missing, it will be imputed using the imputation rules specified in [Section 11.2](#). A completely missing AE stop date will not be imputed and therefore no duration will be calculated in these cases.

The number of days to onset and the duration of each respective related AEs will be summarized by SOC and PT using the mean, SD, min, max and median. These summaries are at the event level so that subjects will be counted once for each multiple related AE they experience. Related AEs with onset >21 days after the most recent treatment will be listed.

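### With the AE start month missing, SAP Table 8 can impute a start after the recorded stop, giving false late onsets and negative durations

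*SAP*

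**What the plan says.** SAP 11.2, Table 8, covers AE and medication dates together. For a start date:

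- **Month, or day and month, missing.** June is used, as in "01-UNK-2023 becomes 01-JUN-2023", provided the result is on or after Baseline treatment; "otherwise, the subsequent month after study treatment will be used". The fallback names no day.
- **Year missing** (alone or with day or month). The first branch is "Assign to year of Baseline study treatment (i.e., 01-JAN-UNK becomes 01-JAN-2019"), again only if that is not before treatment; "otherwise, the date of Baseline study treatment will be used". (The year 2019 in that example cannot arise under a protocol effective in May 2023, but it does not affect this point.)
- **Everything missing.** The Baseline treatment date is used.

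For an end date with the month missing: "Assign to the subsequent month after the start date". A wholly missing end date is not imputed.

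SAP 10.2.4 uses the imputed start in two derivations: "Time to onset of an AE will be derived as the AE start date minus the date of most recent prior treatment", and "Duration of an AE will be derived as the AE stop date minus the AE start date + 1". Both are summarised for related AEs by mean, SD, minimum, maximum and median. In addition, "Related AEs with onset >21 days after the most recent treatment will be listed". Neither 10.2.4 nor Table 8 says what to do when a duration comes out at zero or less.

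**The concern.** Most injection reactions start early; Protocol 5.3.3 expects them to resolve within two to four weeks. If the site knows when such an event ended but not the month it began, the stop date is the best evidence on the start, and the missing-month rule does not use it.

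The table is also uneven. A start about which nothing is known goes to the treatment date, which is sensible for an injection study. A start whose year is correctly recorded can go to a date after the event ended, so more information gives a worse date. The direction also runs against SAP 11.1, where missing intensity, relationship and seriousness take the most severe value: a late imputed start moves a reaction away from the injection that may have caused it.

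At stake are the onset and duration summaries for related AEs and the listing of onsets over 21 days. All are descriptive safety outputs.

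**Working it through.** **Plan's own example.** 01-UNK-2023 gives 01-Jun-2023 if Baseline treatment was on or before that day. This reproduces Table 8. For a later Baseline in 2023 the same entry goes to the fallback.

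**Formulas (SAP 10.2.4).** Onset = start - most recent treatment. Duration = stop - start + 1.

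**Missing month: hand cases.**

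1. *Day and month missing.* Treated 12-Sep-2023, start UNK-UNK-2023, stop 20-Sep-2023. June 2023 precedes treatment, so the month is October 2023.
   - First-of-month reading: start 01-Oct-2023, onset 19 days, duration 20-Sep - 01-Oct + 1 = -10 days.
   - Treatment-day reading: start 12-Oct-2023, onset 30 days, duration -21 days.
   - The event cannot have lasted more than 9 days (12 to 20 September inclusive).
2. *Month missing, fallback.* Treated 10-Aug-2023, true start 11-Aug, stop 20-Aug, recorded 11-UNK-2023. Keeping the day gives 11-Sep-2023: 31 days late, onset 32 days, duration -21 days (true 10).
3. *Month missing, June branch.* Treated 05-Feb-2024, true start 06-Feb, stop 15-Feb, recorded 06-UNK-2024. The rule gives 06-Jun-2024: 121 days late, duration -111 days (true 10).
4. *Recorded year contradicted.* Treated and started 12-Dec-2023, stop 20-Dec-2023, recorded 12-UNK-2023. The fallback gives 12-Jan-2024: 31 days late, duration -22 days.

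**Missing month: simulation.** Table 8 was coded literally and run on 40,000 early reactions per scenario. None of the following assumptions is in the documents:

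- onset 0 to 3 days after the Baseline injection;
- full stop date known;
- true duration uniform on 1-14 or 14-28 days;
- treatment dates over a full calendar year, June-September 2023 or September-December 2023.

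The fallback day is unstated, so three readings were tried. Ranges are across scenarios.

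| Reading of the fallback day | Duration zero or less | Onset shown as over 21 days |
|---|---|---|
| Recorded day kept | 71-96% | 72-96% |
| First of month | 22-83% | 24-57% |
| Treatment day | 94-100% | 94-100% |

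Median lateness was 9 to 31 days. The maximum was 31 days for June-September treatment and 152 days where treatment ran into December or fell before June. The recorded year was contradicted in about 24% of cases for September-December treatment, about 8% for year-round treatment and none for June-September.

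**Missing year.** Baseline year is the earliest year a post-treatment AE can have, and the fallback is the treatment date. With the month known, the imputed start is therefore never later than the true one. In the same simulation the error was 0 to 3 days early, with no duration of zero or less. The fault is different: the fallback drops a known day and month. Treated 12-Sep-2023, start 01-FEB-UNK: 01-Feb-2023 precedes treatment, so the start becomes 12-Sep-2023 with onset 0. The only matching date within participation of up to 14 months is 01-Feb-2024, 142 days after treatment.

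**Month and year both missing.** Table 8 gives no month. Only if June is borrowed can the start be late: up to 151 days, with about 41% of durations at zero or less for year-round treatment and 0% in the other two scenarios.

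**End month missing.** Start 10-Oct-2023, stop UNK-UNK-2024. The month after the start is November 2023, which contradicts the recorded 2024; keeping the year instead gives November 2024, 13 months after the start.

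**Alternative start rule, same simulation.** The earliest date agreeing with the recorded parts, on or after treatment and not after the stop, gave 0% durations of zero or less, 0% false onsets over 21 days and 0% year mismatches. The onset error was 0 days with only the month or only the year missing, and 0 to 3 days early with day and month missing.

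**The case against.** **The trigger should be rare.** Sites record the first day with symptoms (Protocol 7.9.8). AEs are asked about at 72 hours, 14 days and 1 month, and the eCRF has checks and queries. Common reactions are also captured in a daily 28-day diary that is reported separately from other AEs. A start with no month but a usable stop date may hardly occur. This stands: the percentages above are conditional on that pattern and are not a rate among all AEs.

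**Artefacts would be visible.** SAP 11.2 shows dates as collected in listings. This stands only in part: the AE listing in SAP 10.2 also carries derived onset and duration, and the summary tables give no such warning.

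**Stronger readings that the documents do not support.**

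- A reader might infer that the missing-year rule also produces late onsets and negative durations. With the month recorded it errs early, never late.
- A reader might infer that Table 8 ignores recorded date parts throughout. The first branch of each start rule keeps them; they are lost in the fallbacks and in the end-month rule.
- A reader might infer that late imputation broadly moves events into the touch-up period. SAP 4.5.2 keeps every AE of a subject without touch-up in the initial period. For touched-up subjects, an imputed start after touch-up is counted from the touch-up, so the event may leave the over-21-day listing instead of entering it.
- Negative durations need a recorded stop date. If the stop month or year is also missing, the end-date rules place the stop after the start.

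**Conclusion.** The point holds for the missing-month start column. With a recorded stop date, both branches can place the start after the stop, and the fallback states no day and can contradict the recorded year. That is certain from the wording.

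The size is less certain. Among simulated early reactions with no start month and a known stop, 22% to 100% had a duration of zero or less. The spread reflects the unstated day, the assumed treatment dates (the documents give a 4-month enrollment period but no calendar) and the assumed true durations. How many real AEs meet these conditions is unknown and probably small. One such event is still enough to make the reported minimum duration impossible.

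Two lesser faults stand beside it: the missing-year start fallback discards a known day and month and errs early, and the end-month rule can contradict a recorded stop year. This is a minor repair to descriptive safety timing. No effectiveness result depends on it.

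**What to change.** For AE dates only, replace the June, subsequent-month and missing-year start fallbacks with:

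> *Impute a partial start date as the earliest date consistent with the recorded parts that is on or after the Baseline treatment date and not after the recorded stop date.*

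For a missing stop month, keep the subsequent-month rule only where it agrees with the recorded stop year; otherwise use the earliest month in that year that is on or after the start. In the end-month example this gives January 2024. State the day to use when it too is missing; Table 8's own last-of-month convention is available.

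Do not instead set the stop to the latest possible date up to the last visit. In that example, with a last visit on 13-Aug-2024, it would give a duration of 309 days. It would also clash with Protocol 7.9.7.1, which follows related AEs past the end of participation.

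The cost is one table edit and one date-imputation macro. The downside is that some imputed onsets become earlier. That is conservative for relating an AE to the injection, but it can lengthen a duration or take a truly late event off the over-21-day listing. For example, treated 12-Sep-2023, start UNK-UNK-2023, stop 20-Dec-2023 would be imputed to the treatment date, with onset 0 and duration 100 days. A footnote counting AEs with imputed starts would show how much this matters.
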